## 7.2 NCI-IRB REPORTING

### 7.2.1 NCI-IRB Expedited Reporting of Unanticipated Problems and Deaths

The Protocol PI will report to the NCI-IRB:

- All deaths, except deaths due to progressive disease
- All protocol deviations
- All unanticipated problems
- All non-compliance

Reports must be received by the NCI-IRB within 7 working days of PI awareness via iRIS.

### 7.2.2 NCI-IRB Requirements for PI Reporting at Continuing Review

The protocol PI will report to the NCI-IRB:

1. A summary of all protocol deviations in a tabular format to include the date the deviation occurred, a brief description of the deviation and any corrective action.

**Confidential**

*Abbreviated Title: Phase I MVA-Brachyury-TRICOM*

*Version Date: September 14, 2016*

2. A summary of any instances of non-compliance
3. A tabular summary of the following adverse events:
  - All Grade 2 **unexpected** events that are possibly, probably or definitely related to the research;
  - All Grade 3 and 4 events that are possibly, probably or definitely related to the research;
  - All Grade 5 events regardless of attribution;
  - All serious events regardless of attribution.

**NOTE:** Grade 1 events are not required to be reported.

### 7.2.3 NCI-IRB Reporting of IND Safety Reports

Only IND Safety Reports that meet the definition of an unanticipated problem will need to be reported to the NCI IRB.

## 7.3 IND SPONSOR REPORTING CRITERIA

An investigator must **immediately** report to the sponsor, using the mandatory MedWatch form 3500a, any serious adverse event, whether or not considered drug related, including those listed in the protocol or investigator brochure and must include an assessment of whether there is a reasonable possibility that the drug caused the event.

Study endpoints that are serious adverse events (e.g. all-cause mortality) must be reported in accordance with the protocol unless there is evidence suggesting a causal relationship between the drug and the event (e.g. death from anaphylaxis). In that case, the investigator must immediately report the death to the sponsor.

Events will be submitted to [name], authorized representative for the IND Sponsor (CCR) at:

[name].

[name]

[name]

[name]

[contact]

[contact]

Copy all MedWatch forms to: [[contact]](mailto:[contact])

### 7.3.1 Reporting Pregnancy

#### 7.3.1.1 Maternal exposure

If a patient becomes pregnant during the course of the study, the study treatment should be discontinued immediately and the pregnancy reported to the Sponsor. The potential risk of

**Confidential**

*Abbreviated Title: Phase I MVA-Brachyury-TRICOM*

*Version Date: September 14, 2016*

exposure of the fetus to the investigational agent(s) or chemotherapy agents (s) should be documented in box B5 of the MedWatch form “Describe Event or Problem”.

Pregnancy itself is not regarded as an SAE. However, as patients who become pregnant on study risk intrauterine exposure of the fetus to agents which may be teratogenic, the CCR is requesting that pregnancy should be reported in an expedited manner as **Grade 3 “Pregnancy, puerperium and perinatal conditions - Other (pregnancy)”** under the *Pregnancy, puerperium and perinatal conditions* SOC.

Congenital abnormalities or birth defects and spontaneous miscarriages should be reported and handled as SAEs. Elective abortions without complications should not be handled as AEs. The outcome of all pregnancies (spontaneous miscarriage, elective termination, ectopic pregnancy, normal birth, or congenital abnormality) should be followed up and documented.

If any pregnancy occurs in the course of the study, then the investigator should inform the Sponsor within 1 day, i.e., immediately, but **no later than 24 hours** of when he or she becomes aware of it.

The designated Sponsor representative will work with the investigator to ensure that all relevant information is provided to the Sponsor within 1 to 5 calendar days for SAEs and within 30 days for all other pregnancies.

The same timelines apply when outcome information is available.

### 7.3.2 Paternal exposure

Male patients should refrain from fathering a child or donating sperm during the study and for 4 months after the last dose of vaccine.

Pregnancy of the patient’s partner is not considered to be an AE. However, the outcome of all pregnancies (spontaneous miscarriage, elective termination, ectopic pregnancy, normal birth, or congenital abnormality) occurring from the date of the first dose until 4 months after the last dose should, if possible, be followed up and documented.

## 7.4 FDA REPORTING CRITERIA

### 7.4.1 IND Safety Reports to the FDA (Refer to 21 CFR 312.32)

The Sponsor will notify the FDA of any unexpected fatal or life-threatening suspected adverse reactions as soon as possible but no later than 7 calendar days of initial receipt of the information using the MedWatch Form 3500a.

The Sponsor is also responsible for reporting any:

- suspected adverse reaction that is both serious and unexpected
- any findings from clinical, epidemiological, or pooled analysis of multiple studies or any findings from animal or *in vitro* testing that suggest a significant risk in humans exposed to the drug

*Abbreviated Title: Phase I MVA-Brachyury-TRICOM*

*Version Date: September 14, 2016*

- clinically important increase in the rate of a serious suspected adverse reaction over that listed in the protocol or investigator brochure.

to the FDA and to all investigators no later than 15 calendar days after determining that the information qualifies for reporting using the MedWatch Form 3500a. If FDA requests any additional data or information, the sponsor must submit it to the FDA as soon as possible, but no later than 15 calendar days after receiving the request.

#### 7.4.2 FDA Annual Reports (Refer to [21 CFR 312.33](#))

The study Sponsor will submit a brief report annually of the progress of the trial within 60 days of the anniversary date that the IND went into effect as indicated in 21CFR 312.33, and any associated FDA correspondences regarding the IND annual report.

#### 7.4.3 Expedited Adverse Event Reporting Criteria to the IND Manufacturer

The Sponsor will notify the IND Manufacturer of any unexpected fatal or life-threatening suspected adverse reactions as soon as possible but no later than 3 calendar days of initial receipt of the information. The Sponsor will also notify the IND Manufacturer of Serious Adverse Events meeting any of the criteria defined by the bulleted list in Section **7.4.1** no later than 7 calendar days after determining that the information qualifies for reporting. A copy of the draft MedWatch Form 3500a may be used to meet these reporting requirements. Notifications will be sent to the IND Manufacturer's Pharmacovigilance department either via email at [[contact]](mailto:[contact]) or via fax at [contact].

A listing of all other Adverse Events will be provided to the IND Manufacturer annually, e.g. via provision of a copy of the IND annual report which includes a safety summary and Adverse Event Listings. The safety database for this study also will be shared with the IND manufacturer at the end of the study.

### **7.5 NIH OFFICE OF SCIENCE POLICY (OSP)/INSTITUTIONAL BIOSAFETY COMMITTEE (IBC) REPORTING CRITERIA**

#### 7.5.1 Serious Adverse Event Reports to OSP/IBC

The Principal Investigator will notify OSP via email ([[contact]](mailto:[contact])) and IBC of any unexpected fatal or life-threatening experience associated with the use of MVA-brachyury-TRICOM as soon as possible but in no event later than 7 calendar days of initial receipt of the information. Serious adverse events that are unexpected and associated with the use of the MVA-brachyury-TRICOM, but are not fatal or life-threatening, must be reported to NIH OSP/IBC as soon as possible, but not later than 15 calendar days after the sponsor's initial receipt of the information. Adverse events may be reported by using the Adverse Event Reporting template available on the NIH OSP website at: <http://osp.od.nih.gov/office-biotechnology-activities/biomedical-technology-assessment/hgt/gemcris> or by using the FDA Form 3500a.

*Abbreviated Title: Phase I MVA-Brachyury-TRICOM*

*Version Date: September 14, 2016*

### 7.5.2 Annual Reports to OSP/IBC

The study Principal Investigator will submit to OSP via email ([[contact]](mailto:[contact])) and IBC a brief report annually of the progress of the trial within 60 days of the anniversary date that the IND went into effect unless the IND sponsor has been authorized to submit this report.

Within 60 days after the one-year anniversary of the date on which the investigational new drug (IND) application went into effect, and after each subsequent anniversary until the trial is completed, the Principal Investigator (or delegate) shall submit the information described below. Alternatively, the FDA annual report can be sent to OSP/IBC in lieu of a separate report. Please include the OSP/IBC protocol number on the annual report, and the updated clinical protocol.

#### 7.5.2.1 Clinical Trial Information

A brief summary of the status of each trial in progress and each trial completed during the previous year. The summary is required to include the following information for each trial:

- the title and purpose of the trial
- clinical site
- the Principal Investigator
- clinical protocol identifiers, including the NIH OSP/IBC protocol number, NIH grant number(s) (if applicable), and the FDA IND application number;
- participant population (such as disease indication and general age group, e.g., adult or pediatric);
- the total number of participants planned for inclusion in the trial; the number entered into the trial to date whose participation in the trial was completed; and the number who dropped out of the trial with a brief description of the reasons
- the status of the trial, e.g., open to accrual of subjects, closed but data collection ongoing, or fully completed,
- if the trial has been completed, a brief description of any study results.

#### 7.5.2.2 Progress Report and Data Analysis

Information obtained during the previous year's clinical and non-clinical investigations, including:

- a narrative or tabular summary showing the most frequent and most serious adverse experiences by body system
- a summary of all serious adverse events submitted during the past year
- a summary of serious adverse events that were expected or considered to have causes not associated with the use of the gene transfer product such as disease progression or concurrent medications
- if any deaths have occurred, the number of participants who died during participation in the investigation and causes of death

*Abbreviated Title: Phase I MVA-Brachyury-TRICOM*

*Version Date: September 14, 2016*

7.5.2.3 a brief description of any information obtained that is pertinent to an understanding of the gene transfer product's actions, including, for example, information about dose-response, information from controlled trials, and information about bioavailability.

7.5.2.4 A copy of the updated clinical protocol including a technical abstract.

## **7.6 DATA AND SAFETY MONITORING PLAN**

### **7.6.1 Principal Investigator/Research Team**

The clinical research team will meet on a regular basis (at least every other week) when patients are being actively treated on the trial to discuss each patient. Decisions about dose level enrollment and dose escalation if applicable will be made based on the toxicity data from prior patients.

All data will be collected in a timely manner and reviewed by the principal investigator or a lead associate investigator. Adverse events will be reported as required above. Any safety concerns, new information that might affect either the ethical and or scientific conduct of the trial, or protocol deviations will be immediately reported to the IRB using iRIS and to the Sponsor.

The principal investigator will review adverse event and response data on each patient to ensure safety and data accuracy. The principal investigator will personally conduct or supervise the investigation and provide appropriate delegation of responsibilities to other members of the research staff.

### **7.6.2 Sponsor Monitoring Plan**

This trial will be monitored by personnel employed by Harris Technical Services on contract to the NCI, NIH. Monitors are qualified by training and experience to monitor the progress of clinical trials. Personnel monitoring this study will not be affiliated in any way with the trial conduct.

At least 25% of enrolled patients will be randomly selected and monitored at least biannually or as needed, based on accrual rate. The patients selected will have 100% source document verification done. Additional monitoring activities will include: adherence to protocol specified study eligibility, treatment plans, data collection for safety and efficacy, reporting and time frames of adverse events to the NCI IRB and FDA, and informed consent requirements. Written reports will be generated in response to the monitoring activities and submitted to the Principal investigator and Clinical Director or Deputy Clinical Director, CCR, NCI.

### **7.6.3 Safety Monitoring Committee (SMC)**

This protocol will require oversight from the Safety Monitoring Committee (SMC). Initial review will occur as soon as possible after the annual NCI-IRB continuing review date. Subsequently, each protocol will be reviewed as close to annually as the quarterly meeting schedule permits or more frequently as may be required by the SMC. For initial and subsequent reviews, protocols will not be reviewed if there is no accrual within the review period. Written outcome letters will be generated in response to the monitoring activities and submitted to the Principal investigator and Clinical Director or Deputy Clinical Director, CCR, NCI.

**Confidential**

*Abbreviated Title: Phase I MVA-Brachyury-TRICOM*

*Version Date: September 14, 2016*

## **8 STATISTICAL CONSIDERATIONS**

This study will be conducted as a standard phase I trial with an expanded cohort at the MTD. There are 3 dose levels of vaccine to be evaluated, and initially 3 patients will be enrolled in the lowest dose level. If 0/3 have a dose limiting toxicity (DLT) after 28 days from the third patient receiving the initial vaccine on study, then subsequent patients will be accrued to the next higher dose level. If 1/3 has a DLT, then 3 additional patients will be enrolled at that dose level. If 1/6 has a DLT, escalation may proceed, while if 2+/6 have a DLT, then the MTD will be considered to have been exceeded, and up to 3 additional patients will be enrolled at the next lower dose level if 6 patients have not previously been enrolled at that dose. The MTD will be the dose level at which no greater than 1/6 patients has a DLT, and the next higher dose level has at least 2 patients with a DLT.

The MTD will initially consist of 6 patients as indicated, and the study plans to enroll a total of 10 additional patients each at the MTD and the dose level below MTD (total of 16 at the MTD and up to 16 at the dose level just below the MTD) in an effort to identify significant changes in T-cell precursors will be detectable. Potential evaluation techniques include flow-cytometry based intracellular cytokine staining after bBrachyury 15-mer stimulation and ELISPOT. Evaluations will take place both with respect to absolute change as well as whether a positive response is identified.

Because we will be using new evaluation techniques with a first in human study, we will enroll 10 patients in an expansion cohort, resulting in 16 potential evaluable patients in the two highest tolerated dose level cohorts, which will provide 80% power to detect a change in T-cell precursors from baseline equal to 1.0 standard deviations of the difference (effect size = 1.0) using a 2-tailed 0.05 alpha level paired t-test. All 10-16 patients in each dose level with evaluable T-cell precursor data at this dose level will be included in the analysis, with 10 patients providing an illustration of 80% power based on that minimal number. The actual power could be greater than 80% if 11-16 patients are evaluable for this determination. In practice, a nonparametric Wilcoxon signed rank test will be used. A positive response using the flow based intracellular cytokine staining assay will be defined as the frequency of T lymphocytes positive for a cytokine or CD107a post-vaccine being increased greater than two-fold compared to both (1) pre-vaccine values and (2) HLA control post-vaccine; the fraction of the patients who have a positive response out of those evaluable for this determination will be noted and reported along with a corresponding 95% confidence interval.

Although the MTD will have been declared after 6 patients at that dose level have been evaluated, monitoring for toxicity in the additional cohort of patients will continue. In the event that more than one third of all patients enrolled at the MTD experience a DLT, protocol modifications will be undertaken to reduce the likely level of toxicity in future patients prior to continuing to enroll additional subjects.

Clinical response evaluation will take place in the patients enrolled at the MTD and the expansion cohort. The results will be considered secondary and will be used to determine the parameters for a subsequent phase II trial should the preliminary findings from this trial warrant further investigation.

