### **3 STUDY IMPLEMENTATION**

#### **3.1 STUDY DESIGN**

This is an open-label phase I trial with sequential cohorts of patients (3–6 patients per dose cohort to establish safety) with dose escalation of MVA-brachyury-TRICOM vaccine (see Section 8). Three cohorts will receive MVA-brachyury-TRICOM vaccine administered subcutaneously as either 1, 2, or 4 injections of study drug (1 injection =  $2 \times 10^8$  IU) at monthly (28 days– 4 days up to +14 days) intervals for 3 months (treatment). A dose will be considered missed if not given within 14 days of the original schedule and the patient will resume treatment with the next scheduled dose. The time of patient monitoring post injection would be 2 hour observation after first dose and 30 minutes after subsequent doses.

Toxicity in the 28 days following the first vaccination after the 3rd subject (or 6th subject, if applicable) in dose levels 1 through 3 will be employed for decision-making (i.e., for dose-escalation and for maximum tolerable dose estimation). Inpatient dose escalation will not be allowed. In addition, patients may be enrolled as an expansion cohort at the MTD and at the dose level just below the MTD after either 0 of 3 or no more than 1 of 6 patients have been treated at that dose level and have not experienced a DLT for at least 28 days. Cohorts 2 and 3 will accrue up to an additional 10 evaluable patients each (up to 16 patients total in each) for safety and correlative analysis.

Patients will be sequentially enrolled and monitored for safety as described at dose level 2 and dose level 3. If 0 of 3 or no more than 1 of 6 patients treated at each dose level have experienced a DLT for at least 28 days, we will enroll patients on the expansion phases.

Patients may be concurrently enrolled in the expansion cohort of dose level 2 while enrolling patients on dose level 3 for safety evaluation. Any patient who is eligible will be prioritized into a dose escalation slot. Once all dose escalation slots are filled, patients will be enrolled sequentially onto the expansion phase 2, followed by phase 3. Expansion slots will only be filled by subjects who are not eligible (due to concurrent therapy) for escalation slots until safety is established in both dose level 2 and 3. There will not be randomization.

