##### **5.1.1.2 Immunologic /correlative testing will include:**

- Specific T-cell responses, evaluated using flow cytometry intracellular staining (ICS) of CD4 and CD8 T lymphocytes for cytokines including IFN- $\gamma$ , tumor necrosis factor, and IL-2. Additional markers of specific T-cell activation may be included based on evolving results with this assay.
- CD3, CD4, CD8, and CD19 subsets, NK markers, and CD4:CD8 ratio (baseline, about day 29, and about day 85).
- Analysis for cytokines (IFN- $\gamma$ , IL-10, IL-12, IL-2, IL-4, TGF- $\beta$ , etc.), chemokines, antibodies (including yeast and brachyury), TAAs and/or other markers.
- If sufficient samples are available pre- and post-vaccination, PBMCs will be evaluated as follows:
  - a. IFN- $\gamma$  ELISPOT assays for brachyury-specific T lymphocytes using a brachyury-specific peptide in selected HLA-A2 peptides.
  - b. A proliferation assay using brachyury protein in selected patients.
  - c. Phenotypic and functional analysis of immune cell subsets (NK cells and Tregs).
  - d. For use in a circulating tumor cell analysis in collaboration with Epic Sciences, Inc. ([name], [contact]).

*Abbreviated Title: Phase I MVA-Brachyury-TRICOM*

*Version Date: September 14, 2016*

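### Does the 80% power for T-cell change need a named assay, T-cell subset, marker and visit before it can stand?

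*Combined protocol and SAP*

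**What the plan says.** The only primary objective is safety and tolerability (Section 1.1.1). CD8 and CD4 response is a secondary objective (Section 1.1.2).

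Section 8 adds up to 10 patients at each of two dose levels "in an effort to identify significant changes in T-cell precursors will be detectable"; Section 3.1 describes the same enrolment as "up to an additional 10 evaluable patients each (up to 16 patients total in each) for safety and correlative analysis". The power statement is "which will provide 80% power to detect a change in T-cell precursors from baseline equal to 1.0 standard deviations of the difference", at two-sided 0.05 with a paired t-test. The sentence mentions 16 patients, but the next one makes clear that 80% belongs to the minimum of 10. The test used in practice is the Wilcoxon signed rank test.

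On assays, Section 8 says "Potential evaluation techniques include flow-cytometry based intracellular cytokine staining after bBrachyury 15-mer stimulation and ELISPOT". Section 5.1.1.2 puts intracellular cytokine staining (ICS) first and without condition, "evaluated using flow cytometry intracellular staining (ICS) of CD4 and CD8 T lymphocytes for cytokines including" IFN-gamma, tumor necrosis factor and IL-2, and adds "Additional markers of specific T-cell activation may be included based on evolving results with this assay". ELISPOT is run only if enough sample is available.

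A positive response by ICS is "the frequency of T lymphocytes positive for a cytokine or CD107a post-vaccine being increased greater than two-fold compared to both" of two comparators: "1) pre-vaccine values and (2) HLA control post-vaccine". The fraction of evaluable patients who respond is reported with a 95% confidence interval. The Study Calendar (Section 3.3) draws immunology blood at baseline, days 29, 57 and 85, and then from day 169 onward.

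**The concern.** A power figure and an alpha level have an exact meaning only for an identified comparison. Section 8 links neither candidate assay to the powered test, does not choose between CD4 and CD8, fixes no marker gate and names no post-vaccine visit. It gives no multiplicity rule. In the response rule, any cytokine counts, the visit is simply after vaccination, and Section 5.1.1.2 allows markers to be added.

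If the gate and visit were picked after the results were seen, a nominally significant change would arise by chance more often than 5% of the time, and the responder fraction would grow with the number of markers and visits counted. T-cell change is the endpoint Section 8 uses to size the expansions, which are up to 20 of at most 38 patients, so this deserved a check.

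**Working it through.** **1. The plan's own figure.** Inputs from Section 8: standardized change d = 1.0, two-sided alpha 0.05, n = 10. For a paired t-test, power = P(|T| > t₀.₉₇₅,ₙ₋₁), where T is noncentral t with n − 1 degrees of freedom and noncentrality d√n.

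- n = 10: critical value 2.262, noncentrality √10 = 3.162, power **80.3%**. The stated 80% is reproduced.
- n = 16: critical value 2.131, noncentrality 4, power 96.2%. This confirms that the 80% refers to 10 patients.

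Wilcoxon signed rank test, exact critical values, simulated normal differences: at n = 10, reject if the smaller rank sum is 8 or less (actual size 4.88%), power about 78.5%; at n = 16, about 95%.

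**2. What the choice of comparison could do to the error rate.** The number of tests is an assumption; the documents do not state one. With k independent tests of size 0.0488 at n = 10, the chance of at least one false positive is 1 − (1 − 0.0488)^k. Readouts from the same patient are likely to be positively correlated, which lowers it. The last column is simulated with no vaccine effect, readout correlation 0 to 0.8, and a shared baseline where there are several visits.

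| Assumed set per dose level | k | Independent | Simulated range |
|---|---|---|---|
| One named comparison | 1 | 4.9% | 4.9% |
| CD4 and CD8, one visit | 2 | 9.5% | 8–10% |
| One gate, three visits | 3 | 13.9% | 10–13% |
| Two subsets × three visits, or two subsets × three cytokines | 6 | 25.9% | 15–26% |

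Larger sets come from multiplying the marker list by the blood-draw calendar: 2 × 3 × 3 = 18 tests gives 29–56%, and 2 × 4 × 3 = 24 tests gives 33–66%. These are worst cases. A draw schedule is not an analysis plan, and no text says each cell will be tested at 0.05.

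**3. The positive-response rule.** Assume no true change and lognormal pre-vaccine, post-vaccine and control values with equal means, all independent. A false response needs the post-vaccine value to exceed twice both comparators. The assay coefficient of variation (CV) is not in the documents, so a range is shown. Expected false responders among 16 patients:

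| Assay CV (assumed) | One marker, one visit | Four markers, one visit |
|---|---|---|
| 20% | 0.0 | 0.05 |
| 30% | 0.2 | 0.7 |
| 50% | 0.9 | 3.4 |

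The four-marker column treats markers as independent; correlation of 0.5 between them lowers the last two entries to about 0.6 and 2.7. Counting eight readouts at any of three visits would give 0.3, 3–4 and 9–12, but that needs CD4 and CD8 to be scored separately and every visit to count, neither of which the rule says.

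**4. What a tighter rule would cost.** Suppose CD4 and CD8 were co-named at 0.025 each. Power for a change of 1.0 SD at n = 10 falls to 68% (t-test) or 61% (Wilcoxon). At n = 13 it is 84% or 79.9%. Under Section 3.1 an expansion may open after 0 of 3 patients have a dose-limiting toxicity, so a dose level may hold only 3 + 10 = 13 patients, with no room for a non-evaluable one.

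**The case for a change.** The best argument for a change is that Section 8 does more than describe. It states an alpha and a power, plans a hypothesis test, and reports a response fraction with a confidence interval. Even the smallest multiple reading, CD4 and CD8 at one visit, nearly doubles the nominal 5%. A few added sentences would need no new visits or samples.

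The factual part stands: subset, gate and visit are open for the powered test, and cytokine list and visit are open for the response rule. What does not follow is that a stated figure or rule is wrong. The 80% is correct, and the power statement speaks of a single change from baseline. It would be too strong to say no assay is named: two are, ICS is fixed for the response rule, and ELISPOT is conditional on sample. The allowance for extra markers may mean assay development rather than selection on trial results, and a late marker that is not a cytokine would not count under the response rule.

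Nor is the remedy a plain correction. It would be a set of blanks for the sponsor to fill, and the choice between one test and two at 0.025 is a trade-off that could cost power at the planned minimum.

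**Conclusion.** The gap is real but minor, and no change to the plan is called for. The power figure is right for one paired comparison at 10 patients (80.3%, or about 78.5% by Wilcoxon). The T-cell endpoint is secondary, new assay methods are being used in a first-in-human study, and no escalation, dose choice or go/no-go rule depends on reaching p < 0.05. The response rule already has a fixed assay, a two-fold threshold and two comparators.

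Analysts can fill the rest sensibly: treat ICS as the lead assay, state the subset, markers and visit behind each result, and report the other readouts descriptively. A reader who sees several readouts should take a lone p < 0.05 as suggestive. On the modest readings in the table (two to six tests) its chance under no effect is roughly 8–26%, not 5%. Those figures rest on assumed test counts and correlations. The responder figures rest on an assumed assay CV and are near zero at 20% for one or four markers at one visit. The conclusion would differ if a dose choice or a claim of efficacy were tied to this test; the documents tie neither to it.

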**Confidential**

*Abbreviated Title: Phase I MVA-Brachyury-TRICOM*

*Version Date: September 14, 2016*

- If 2 or more patients experience DLT on a dose level, then the MTD has been exceeded and dose escalation has been completed. Three patients will be enrolled on the dose level below that level, provided that not more than 3 patients were treated on that dose level.

(The MTD will be the dose level at which no greater than 1/6 patients has a DLT, and the next higher dose level has at least 2 patients with a DLT.)

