### 3.1.3 Schema

Dose Level	Dose and Schedule
1 N = 3 to 6	1 site of injection at $2 \times 10^8$ IU given every 28 days for 3 doses.
2 N = 10-16	2 sites of injection at $2 \times 10^8$ IU given every 28 days for 3 doses.
3 N = 10-16	4 sites of injection at $2 \times 10^8$ IU given every 28 days for 3 doses.

Dose escalation will proceed in cohorts of 3–6 patients. The MTD is the dose level at which no more than 1 of up to 6 patients have DLT during the first 28 days of treatment, and the dose below that at which at least 2 (of  $\leq 6$ ) patients have DLT as a result of the drug. If a patient did not experience DLT and did not complete the DLT evaluation period (28 days), he or she will not be evaluable for toxicity and will be replaced in the dose level as outlined in the Statistical Design (Section 8).

Dose escalation will follow the rules outlined in the table below.

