**Confidential**

*Abbreviated Title: Phase I MVA-Brachyury-TRICOM*

*Version Date: September 14, 2016*

Number of Patients with DLT at a Given Dose Level	Escalation Decision Rule
0 of 3	Enter up to 3 patients at the next dose level
$\geq 2$	Dose escalation will be stopped. This dose level will be declared the maximally administered dose (highest dose administered). Up to three (3) additional patients will be entered at the next lowest dose level if only 3 patients were treated previously at that dose.
1 of 3	Enter up to 3 more patients at this dose level. 
 
• If 0 of these 3 patients experience DLT, proceed to the next dose level.
 
• If 1 or more of this group experience DLT, then dose escalation is stopped, and this dose is declared the maximally administered dose. Up to three (3) additional patients will be entered at the next lowest dose level if only 3 patients were treated previously at that dose.
 

$\leq 1$ of 6 at highest dose level below the maximally administered dose	This is the MTD and is generally the recommended phase II dose. At least 6 patients must be entered at the recommended phase II dose.

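### The only numeric DLT trigger for the expansion phase covers the MTD alone, although two dose levels are expanded

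*Combined protocol and SAP*

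**What the plan says.** Section 8 continues toxicity monitoring after escalation and adds one numeric rule: "In the event that more than one third of all patients enrolled at the MTD experience a DLT, protocol modifications will be undertaken". No other section gives a DLT rate for the expansion phase.

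The Précis, Section 3.1 and Section 8 all expand two levels. Section 3.1 states that "patients may be enrolled as an expansion cohort at the MTD and at the dose level just below the MTD", and names cohorts 2 and 3 with up to 10 further evaluable patients each.

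The MTD is defined by what happens one level up. Section 8 requires at most 1 of 6 with a DLT "and the next higher dose level has at least 2 patients with a DLT". Section 3.1 closes with the same condition ("the next higher dose level has at least 2 patients with a DLT"). Section 3.1.3 words it as "and the dose below that at which at least 2", and its escalation table as "highest dose level below the maximally administered dose". That table adds: "At least 6 patients must be entered at the recommended phase II dose".

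On timing, Section 3.1 says: "Patients may be concurrently enrolled in the expansion cohort of dose level 2 while enrolling patients on dose level 3 for safety evaluation". Until safety is established at both levels, expansion slots go only to patients whose concurrent therapy keeps them out of escalation. Section 2.1.2 lists these therapies: erlotinib, breast-cancer hormonal therapy, HER2-directed therapy, and capecitabine and/or bevacizumab.

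**The concern.** The sponsor judged that a DLT-rate rule was needed once a level is expanded, but tied it to a label that fits at most one of the two levels and that may not yet exist when level 2 expansion opens. This is a first-in-human vaccine with safety as its primary objective. Early level 2 expansion is where patients first receive it alongside other active cancer drugs, and the 3 to 6 escalation patients who clear level 2 largely do not test those combinations. If a combination proved toxic at level 2, no stated DLT rate would oblige the team to pause enrolment and modify the protocol.

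**Working it through.** **Enrolment (Section 8).** 3 levels × 6 + 2 expansions × 10 = 38, which reproduces the plan's maximum. Expansion patients: 20.

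**Who is outside the trigger.**

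| Outcome of level 3 | MTD | Expansion patients outside the trigger |
|---|---|---|
| Clears, taken as the MTD | Level 3 | Up to 10, at level 2 |
| Clears, definition read literally | None: no higher level with 2 DLTs | All 20 |
| Exceeded, level 2 holds | Level 2 | None at level 2; Section 8 would expand level 1, but Section 3.1 does not |

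**Assumptions.** The DLT rate p is assumed throughout, and patients are independent. Level 2 enters expansion at 0/3, 1/6 or 0/6; each start is taken as given, so the results are brackets.

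**Chance that a level clears.** c(p) = (1−p)³ + 3p(1−p)²·(1−p)³.
- p = 0.05: 0.8574 + 0.1161 = 0.9734; all three levels, 0.9734³ = 0.922.
- p = 0.40: 0.2160 + 0.0933 = 0.3093; all three levels, 0.3093³ = 0.0296.

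**DLTs needed to exceed one third.** 2 of 5; 3 of 6–8; 4 of 9–11; 5 of 12–14; 6 of 15–16.

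**Chance that a level 2 trigger fires over 10 expansion patients.** Section 8 sets no checking schedule, so two extremes are shown. For one check at the end, starts of 0/3 (5 of 13 needed) and 1/6 (6 of 16 needed) both require at least 5 DLTs among the 10; a 0/6 start requires at least 6. Checking after every patient uses an exact patient-by-patient recursion.

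| True rate | Every patient: 0/3 or 1/6 | Every patient: 0/6 | Once at end: 0/3 or 1/6 | Once at end: 0/6 |
|---|---|---|---|---|
| 10% | 0.018 | 0.001 | 0.0016 | 0.0001 |
| 20% | 0.105 | 0.015 | 0.033 | 0.006 |
| 40% | 0.512 | 0.225 | 0.367 | 0.166 |

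Only the 40% row lies above the sponsor's threshold and represents lost protection. In the 10% and 20% rows a firing is a false pause, which is a cost of the fix.

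**Joint chance: all levels clear and a level 2 trigger would have fired.**
- Common 40% rate, every patient: 0.0296 × 0.225 = 0.7% to 0.0296 × 0.512 = 1.5%.
- Escalation at 5%, level 2 expansion at 40%, every patient: 0.922 × 0.225 = 21% to 0.922 × 0.512 = 47%.
- Same scenario, one check at the end: 0.922 × 0.166 = 15% to 0.922 × 0.367 = 34%.

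DLT status takes 28 days (Section 3.1.2) and about 3 patients a month are expected (Section 8), so practice would fall between the two schedules.

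**The case against.** **Level 2 expansion is not unguarded.** Toxicity monitoring continues there (Section 8). The team discusses each patient at least every other week and bases dose-level enrolment on prior toxicity (7.6.1). SAEs go to the sponsor immediately (7.3), and unanticipated problems and deaths not due to progression go to the IRB within 7 working days (7.2.1). An attributable grade 5 event halts accrual (3.1.1), a patient with a DLT stops vaccine (3.4.1), and a safety monitoring committee reviews the trial (7.6.3). This stands. A reader might infer that repeated DLTs at level 2 would go unnoticed; the documents do not support that. None of these provisions, however, states a DLT rate.

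**The two-or-more-DLTs bullet in Section 3.1 has no denominator**, so it might seem to cover expansion. The rest of 3.1 ties decisions to the third or sixth subject, and 3.1.3 limits the count to at most 6 patients. It is an escalation rule and does not close the gap.

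**High rates look unlikely.** Section 1.2.14 reports no DLTs in 24 patients on a related MVA-BN vaccine (one-sided 95% upper bound 1 − 0.05^(1/24) = 12%). Section 1.2.9 reports none in a 23-subject study of another brachyury vaccine. In Section 1.2.11, 84 of 215 poxviral-vaccine patients had concurrent treatment, and 19 + 2 = 21 grade 3–4 events were recorded overall. The Précis calls the permitted therapies relatively non-toxic. These are other products and mostly other partner drugs, so the evidence is indirect, but it points well below 40%. This stands, and it is why the point is minor.

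**Conclusion.** The gap is real but minor. Section 8's trigger, followed as written, misses up to 10 level 2 expansion patients if level 3 is taken as the MTD, and all 20 expansion patients under the literal definition. What is missing is a DLT rate at which enrolment at that level must pause; oversight itself is present.

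The effect is small unless concurrent therapy pushes the level 2 DLT rate above one third. Under the stated assumptions it is 0.7–1.5% at a common 40% rate, and 15–47% only with a rise from 5% to 40%.

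Two stronger readings are tempting. A reader might count firings at true rates of 10–30% as lost protection; those rates lie below the threshold, so such firings are false alarms. A reader might also infer that escalation decisions or the T-cell analysis are compromised; neither depends on this trigger.

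**What to change.** In Section 8, make the more-than-one-third rule apply to all patients enrolled at any dose level being expanded, counted separately by dose level, whether or not an MTD has been declared. Keep the threshold, and keep the six-patient requirement for the MTD (Section 8 and the 3.1.3 table). Do not add a statement that level 3 becomes the MTD after 0 of 3: Section 8 has the MTD declared only after six patients have been evaluated.

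The change is one sentence, with no extra patients, procedures or dose levels. Its downside is a false pause at level 2. Checked after every patient, the chance is 0.1–1.8% at a 10% DLT rate and 1.5–10.5% at 20%. Checked once after the tenth expansion patient, it is at most 0.2% and 0.6–3.3%.
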